Primary Objectives: 
• Phase 1: To evaluate the safety and tolerability, and define the maximum tolerated dose (MTD) or a pharmacologically active dose (PAD) of epacadostat administered in combination with durvalumab in subjects with select advanced solid tumors.• Phase 2: To evaluate the efficacy of epacadostat administered in combination with durvalumab in subjects with select advanced solid tumors by assessing the objective response rate (ORR) per modified RECIST v1.1 (mRECIST v1.1) at the MTD or PAD.	
Secondary Objectives: 
• Phase 1: To evaluate the efficacy of epacadostat administered in combination with durvalumab in subjects with select advanced solid tumors by assessing ORR per mRECIST v1.1.• Phase 2: To evaluate the safety and tolerability of the MTD or PAD of epacadostat administered in combination with durvalumab in subjects with select advanced solid tumors.• Phases 1 and 2: To evaluate the efficacy of epacadostat administered in combination with durvalumab in subjects with select advanced solid tumors by assessing duration of response and progression-free survival (PFS).• Phases 1 and 2: To evaluate the pharmacokinetics (PK) of epacadostat and durvalumab when administered in combination.• Phases 1 and 2: To determine the immunogenicity of durvalumab when administered with epacadostat. 
[REDACTED]
 
[REDACTED]
 
[REDACTED]
 
[REDACTED]
	
Overall Study Design: 
This is a Phase 1/2 open-label study of epacadostat administered in combination with durvalumab in subjects with advanced melanoma, non-small cell lung cancer (NSCLC), pancreatic cancer (Phase 1 only), squamous cell carcinoma of the head and neck (SCCHN), triple-negative breast cancer (TNBC), gastric or gastroesophageal (GE) junction cancer, and transitional cell carcinoma (TCC) of the genitourinary (GU) tract. The dose-escalation part of the study (Phase 1) uses a 3 + 3 design to identify the MTD or PAD of epacadostat in combination with durvalumab. Phase 2 will further explore the safety and efficacy of the MTD or PAD of epacadostat in combination with durvalumab determined in Phase 1. More than 1 PAD may be evaluated in Phase 2.
	

Phase 1 Dose Escalation

Phase 1 is the dose-escalation phase, which will include up to 6 cohorts of subjects treated with epacadostat at doses of 25 mg twice daily (BID), 50 mg BID, 75 mg BID, 100 mg BID, and 300 mg BID in combination with durvalumab 3 mg/kg or 10 mg/kg given on Day 1 of each 14-day cycle. A minimum of 3 subjects will be enrolled and treated in each cohort, and all 3 subjects will be observed for a minimum of 42 days before the subsequent cohort begins enrollment. Subjects must have received the cohort-specific dose of epacadostat for at least 75% of the doses (63 doses) and have received at least 3 doses of durvalumab during the 42-day dose-limiting toxicity (DLT) observation period, or have experienced a DLT to be evaluable for dose tolerability. Additional subjects will be enrolled in a cohort to achieve the minimum of 3 evaluable subjects if dropouts or dose interruptions/reductions occur that result in a subject being nonevaluable for DLTs.

The dose of epacadostat will be escalated if 0 of the first 3 evaluable subjects enrolled experience a DLT. If 1 of the first 3 evaluable subjects enrolled experience a DLT, the cohort will be expanded to include 3 additional evaluable subjects. If 2 or more of either 3 or 6 subjects enrolled experience a DLT, the prior dose level will be considered the MTD. If only 3 subjects were treated at this dose level, the dose will be confirmed as the MTD by evaluation of an additional 3 subjects before this dose is recommended for Phase 2 testing.

The cohorts and dose levels are shown in the table below.

Cohort	Maximum Daily Dose of Epacadostat	Dose of Durvalumab (Once Every 14 Days)
1	25 mg BID orally	3 mg/kg IV
2	25 mg BID orally	10 mg/kg IV
3	50 mg BID orally	10 mg/kg IV
4	75 mg BID orally	10 mg/kg IV
5	100 mg BID orally	10 mg/kg IV
6	300 mg BID orally ^a	10 mg/kg IV

IV = intravenous.

^a Intermediate dose levels may be explored based on emerging PK or pharmacodynamic data.

Phase 2

Approximately 140 to 192 subjects with advanced melanoma, NSCLC, SCCHN, TNBC, gastric or GE junction cancer, or TCC of the GU tract will be enrolled at the MTD or PAD of epacadostat in combination with durvalumab. The approximate number of subjects needed for the melanoma, TNBC, and gastric and GE junction cancer cohorts will be determined using the Simon 2-stage design: Stage 1 will be the initial number of subjects per tumor type, and the decision to proceed with Stage 2 will be determined by the response rate observed in Stage 1. If more than 1 PAD is evaluated, the cohort may or may not be repeated for the specified tumor type as indicated in the table below. The sponsor may limit enrollment of a specific tumor type to Stage 1.

Tumor Type	No. of Subjects Enrolled		
	Stage 1	Stage 2 (If Study Proceeds to Stage 2)	Total (Stage 1 + 2)
Melanoma	15	25	40
TNBC	13	16	29
Gastric and GE junction cancer	9	11	20

Under Amendment 6, enrollment of the NSCLC, SCCHN, and TCC of the GU tract cohorts will be completed as expansion cohorts at the 300 mg BID dose level. The sample size for each cohort will be increased to account for the heterogeneity of PD-1 pathway-treated and PD-1 pathway-naive subjects within the selected tumor types. The approximate number of subjects per tumor type is listed in the table

below, and the number of PD-1 pathway–treated subjects in each cohort will be limited to 10 in order to reduce the risk of any cohort having a significant imbalance between PD-1 pathway–treated and PD-1 pathway–naïve subjects, thereby preserving the predicted levels of baseline efficacy observed with PD-1 pathway monotherapy. Subjects enrolled at the 100 mg BID will be analyzed independently.

Tumor Type	No. of Subjects Enrolled	
	100 mg BID ^a (n = 19)	300 mg BID ^b (n = 84)
NSCLC	8	28
SCCHN	7	28
TCC of the GU tract	4	28

^a Subjects enrolled in the 100 mg BID dose level were enrolled before Amendment 5.

^b All subjects in the 300 mg BID NSCLC, SCCHN, and TCC of the GU tract cohorts enrolled in Amendment 5 or earlier are included in the total sample size.

The study will consist of 3 periods:

Screening: Up to 28 days.

Treatment Period: The treatment period will continue every 14 days for up to 12 months as long as subjects are receiving benefit from treatment and have not met any criteria for study withdrawal. Once subjects complete 12 months of study treatment or permanently discontinue study treatment for any other reason, the end-of-treatment (EOT) visit should be conducted, and they should enter the safety follow-up period of the study.

Protocol Amendment 6 (28 JUN 2017) removed the option for subjects to receive epacadostat monotherapy once they completed 12 months of combination therapy with durvalumab. However, subjects already receiving epacadostat monotherapy prior to Amendment 6 were allowed to continue if they were receiving clinical benefit and their investigator felt it was in the best interest of the subject. These subjects will be allowed to continue epacadostat monotherapy for up to an additional 12 months, and their maximum overall study treatment duration should not exceed 24 months. Exceptions for these subjects to continue study treatment beyond 24 months will require medical monitor review and approval every 3 months.

Follow-Up Period: The safety follow-up visits will occur at 42 days and 90 days after the EOT visit or after the last dose of study treatment (if the EOT was not performed).

Study Drugs, Dosages, and Modes of Administration:

Epacadostat will be self-administered orally BID without regard to food and continued BID during each 14-day cycle. The MTD or PAD of epacadostat defined during Phase 1 will be used for Phase 2.

All BID doses will be taken morning and evening, approximately 12 hours apart. If a dose is missed by more than 4 hours, that dose should be skipped and the next dose should be taken at the scheduled time. If the subject vomits, an additional dose should not be taken. Intrasubject dose escalation of epacadostat is not allowed.

Durvalumab is an investigational agent and will be administered at 3 mg/kg or 10 mg/kg over 60 minutes on Day 1 of each 14-day cycle for up to 12 months. There will be an observation period of 3 hours after the first dose of durvalumab is administered. Intrasubject dose escalation of durvalumab is not allowed except as defined in the body of the Protocol.

Reference Therapy, Dosage, and Mode of Administration: Not applicable.

Duration of Participation: Subject participation is expected to average approximately 6 months.

Study Population:

Subjects with histologically or cytologically confirmed advanced melanoma, NSCLC, pancreatic cancer (Phase 1 only), SCCHN, TNBC, gastric or GE junction cancer, or TCC of the GU tract will be enrolled.

Key Inclusion Criteria:

- Male or female subjects, age 18 years or older.
- Histologically or cytologically confirmed diagnosis of melanoma, NSCLC, pancreatic cancer (Phase 1 only), SCCHN, TNBC, gastric or GE junction cancer, or TCC of the GU tract that is locally advanced (not amenable to curative therapy such as surgical resection) or metastatic.
- Must have failed at least 1 prior treatment regimen for locally advanced or metastatic disease or be intolerant to treatment or refuse standard treatment. Investigational agents used in combination with standard therapies are allowed. Adjuvant, neoadjuvant, or chemoradiation regimens given within 6 months of screening would be counted as having received 1 prior systemic regimen and would not require an additional systemic regimen for advanced or metastatic disease.
- For subjects with metastatic melanoma:
 - Must have known V600E activating BRAF mutation status or consent to BRAF V600E mutation testing during screening. Testing should be performed in a CLIA certified laboratory. BRAF mutation status determined as part of a panel of genetic tests performed in a gene expression analysis will also satisfy the inclusion criterion for BRAF mutation testing.
 - May be treatment-naïve or have received prior treatment with an anti-cytotoxic T-lymphocyte-associated antigen 4 (CTLA-4) or anti-programmed cell death receptor 1 (anti-PD-1) targeted agent.
Note: In Phase 1, subjects who are BRAF mutation positive must have received prior treatment with a BRAF inhibitor with or without a MEK inhibitor.
 - Ocular melanoma will be excluded.
- For subjects with NSCLC:
 - Subjects who have tumors with driver mutations (eg, epidermal growth factor receptor [EGFR] mutation positive or anaplastic lymphoma kinase fusion oncogene positive) must have received treatment with a targeted therapy and have progressed or be intolerant, if a targeted agent is available for the specific driver mutation.
 - Subjects may have received prior treatment with an anti-PD-1 targeted agent.
- For subjects with pancreatic cancer (Phase 1 only):
 - Subjects in Phase 1 must have an exocrine pancreatic neoplasm.
Note: Exocrine pancreatic neoplasms include all tumors related to the pancreatic ductal and ancinar cells and their stem cells.
- For subjects with SCCHN:
 - Histology of squamous cell carcinoma.
 - Carcinoma of the nasopharynx and salivary gland will be excluded.
 - Prior systemic regimens must include a platinum-based therapy. Investigational agents used in combination with standard therapies are allowed. Subjects who relapse within 6 months of adjuvant therapy, including a platinum-containing regimen, may enroll.
- For subjects with TNBC:
 - Histologically or cytologically confirmed breast adenocarcinoma that is unresectable or metastatic.
 - Subjects with breast cancer history of different phenotypes (ie, estrogen receptor [ER]/progesterone receptor [PgR]/human epidermal growth factor receptor 2 [HER2] positive) must have pathologic confirmation of triple-negative disease from the most current biopsy.
 - Pathologically confirmed as triple negative, source documented, defined as both of the following:
 - ER and PgR negative: < 1% of tumor cell nuclei is immunoreactive in the presence of evidence that the sample can express ER or PgR (positive intrinsic controls).
 - HER2 negative as per American Society of Clinical Oncology/College of American Pathologists HER2 test guidelines.

Note: HER2 test result should be reported as negative if a single test (or all tests) performed in a tumor specimen show the following:

- Immunohistochemistry (IHC) 1+ as defined by incomplete membrane staining that is faint/barely perceptible and within > 10% of the invasive tumor cells.
- IHC result is 0 as defined by no staining observed or membrane staining that is incomplete and is faint/barely perceptible and within ≤ 10% of the invasive tumor cells.
- In situ hybridization (ISH) assay is negative based on a single probe average HER2 copy number < 4.0 signals/cell or dual probe HER2/CEP17 ratio < 2.0 with an average HER2 copy number < 4.0 signals/cell.
- If results are equivocal, reflex testing (same specimen using the alternative test or new specimen, if available) should be performed using an alternative assay (IHC or ISH).
- For subjects with TCC of the GU tract:
 - Histologically or cytologically confirmed TCC of the bladder, ureter, or renal pelvis or mixed histology bladder cancer.
 - Metastatic or locally advanced and not amenable to curative therapy with disease progression on or after platinum-based chemotherapy or alternative therapy if platinum-based therapy is not appropriate.
- For subjects with gastric or GE junction cancer:
 - Histologically or cytologically confirmed diagnosis of gastric or GE junction adenocarcinoma.
 - Progression on or after therapy containing platinum/fluoropyrimidine.
 - Documentation of HER2/neu status.
- Presence of measurable disease per RECIST v1.1 guidelines.
- ECOG performance status 0 to 1.
- Fresh baseline tumor biopsies (fresh baseline biopsy is defined as a biopsy specimen taken within 28 days prior to Cycle 1 Day 1) are required at baseline, except if inaccessible with medical monitor approval. Archival tissue should also be submitted if available.

Note: If a fresh baseline biopsy is inaccessible, an archival specimen should be submitted.

Key Exclusion Criteria:

- Laboratory and medical history parameters not within the Protocol-defined range. All screening laboratory tests should be performed within 7 days of treatment initiation.
 - Absolute neutrophil count < $1.5 \times 10^9/L$.
 - Platelets < $75 \times 10^9/L$.
 - Hemoglobin < 9 g/dL or < 5.6 mmol/L (transfusion is acceptable to meet this criterion).
 - Serum creatinine $\geq 1.5 \times$ institutional upper limit of normal (ULN) OR measured or calculated creatinine clearance (glomerular filtration rate can also be used in place of creatinine or CrCl) < 50 mL/min for subjects with creatinine levels > $1.5 \times$ institutional ULN.
 - AST or ALT > $2.5 \times$ institutional ULN OR > $5 \times$ ULN for subjects with liver metastases.
 - Total bilirubin > $1.5 \times$ ULN OR direct bilirubin > institutional ULN for subjects with total bilirubin levels > $1.5 \times$ ULN.
 - If there is no institutional normal range available for the direct bilirubin, the direct bilirubin should be < 40% of the total bilirubin.
 - In no case can total bilirubin exceed $3.0 \times$ ULN.
 - International normalized ratio (INR) or prothrombin time (PT) > $1.5 \times$ ULN (unless subject is receiving anticoagulant therapy, then subject may be included as long as PT or INR is within therapeutic range of intended use of anticoagulants).
 - Activated partial thromboplastin time (aPTT) > $1.5 \times$ ULN (unless subject is receiving anticoagulant therapy, then subject may be included as long as aPTT is within therapeutic range of intended use of anticoagulants).

- Current pregnancy or breastfeeding.
- Participation in any other study in which receipt of an investigational study drug occurred within 28 days or 5 half-lives (whichever is longer) prior to first dose. For investigational agents with long half-lives (eg, 5 days), enrollment prior to the fifth half-life requires medical monitor approval.
- Receipt of prior immune checkpoint inhibitors (eg, anti-CTLA-4, anti-programmed cell death receptor 1 [anti-PD-1], anti-programmed cell death ligand 1 [anti-PD-L1], and any other antibody or drug specifically targeting T-cell costimulation) or an indoleamine 2,3-dioxygenase (IDO) inhibitor. Subjects who have received experimental vaccines or other immune therapies should be discussed with the medical monitor to confirm eligibility.

Note: The exception to this exclusion criterion would be subjects who have received a prior anti-CTLA-4 or PD-1 pathway targeted agent for indications in which an anti-CTLA-4 or PD-1 pathway targeted agent has been approved (eg, melanoma). In this case, the subject would be eligible to participate in the study.

- Receipt of an immunologically based treatment for any reason, including chronic use of systemic steroid at doses ≥ 10 mg/day prednisone equivalent within 14 days prior to the first dose of study treatment. Use of inhaled or topical steroids or systemic corticosteroids < 10 mg is permitted.
- Receipt of any anticancer medication in the 21 days prior to receiving the first dose of study medication or any unresolved toxicity $>$ Grade 1 from previous anticancer therapy, except for stable chronic toxicities not expected to resolve, such as peripheral neurotoxicity. Prior treatment with nitrosureas (eg, carmustine or lomustine) require a 6-week washout prior to the first dose of study treatment.
- Untreated central nervous system (CNS) metastases or carcinomatous meningitis, or CNS metastases that have progressed (eg, evidence of new or enlarging CNS metastasis or new neurological symptoms attributable to CNS metastases). Subjects with treated, clinically stable CNS metastases (defined as 2 brain images at least 4 weeks apart, both of which were obtained after treatment to the brain metastases) and who are off all corticosteroids for at least 2 weeks are eligible.
- Any active or inactive autoimmune process or inflammatory disorder (including rheumatoid arthritis, moderate or severe psoriasis, multiple sclerosis, sarcoidosis syndrome, diverticulitis [with the exception of diverticulosis], inflammatory bowel disease, systemic lupus erythematosus, Wegener syndrome [granulomatosis with polyangiitis, Graves' disease, hypophysitis, uveitis, etc]) or receipt of systemic therapy for an autoimmune or inflammatory disease.

Note: Exceptions include subjects with vitiligo, hypothyroidism stable on hormone replacement, controlled asthma, Graves' disease, or Hashimoto's disease, celiac disease controlled by diet alone, or with medical monitor approval. Subjects without active disease in the last 5 years may be included but only after consultation with medical monitor.

- Evidence of interstitial lung disease or active, noninfectious pneumonitis.
- Prior radiotherapy within 2 weeks of therapy. Subjects must have recovered from all radiation-related toxicities, not require corticosteroids, and not have had radiation pneumonitis. A 1-week washout is permitted for palliative radiation to non-CNS disease with medical monitor approval.
- Receipt of monoamine oxidase inhibitors within the 21 days prior to the first dose of study treatment.
- History of serotonin syndrome after receiving 1 or more serotonergic drugs.
- History or presence of an abnormal electrocardiogram (ECG) that, in the investigator's opinion, is clinically meaningful. Screening QTc interval > 480 msec is excluded (corrected by Fridericia or Bazett's formula). In the event that a single QTc is > 480 msec, the subject may be enrolled if the average QTc for the 3 ECGs is ≤ 480 msec. For subjects with an intraventricular conduction delay (QRS interval ≥ 120 msec), the JTc interval may be used in place of the QTc with sponsor approval. The JTc must be < 340 msec if JTc is used in place of the QTc. Subjects with left bundle branch block are excluded.

Study Schedule/Procedures:

Subjects will have regularly scheduled study visits at the clinic site on Day 1 of every cycle (\pm 3 days) where laboratory assessments, vital sign collection, and physical examinations will be performed. Additional visits will be required during Cycle 1 for PK [REDACTED] assessment for subjects in Phase 1. Liver function (chemistry) tests will be performed every 14 days. Assessment of tumor size (by magnetic resonance imaging or computed tomography scan) will be performed at screening or baseline (prior to beginning therapy) and every 12 weeks until the end of treatment. Disease progression should be confirmed by a second, consecutive assessment at least 4 weeks after the first indication of progression per mRECIST v1.1 when the subject is clinically stable.

Fresh tumor biopsies will be required (except as indicated in the inclusion criteria) at baseline [REDACTED]
[REDACTED]

Standard PK parameters (eg, $t_{1/2}$, C_{ss} , V_{ss} , AUC, clearance) will be determined for durvalumab and epacadostat.

Primary Endpoints:

- Phase 1: MTD or PAD. The MTD is defined by the highest dose cohort where no more than 1 of 6 subjects experience a DLT, or the highest Protocol-defined dose for each agent in the absence of exceeding the MTD. Alternatively, the PAD is defined as a tolerated dose of epacadostat (in combination with durvalumab) that produces substantial pharmacologic target inhibition. Safety and tolerability will be assessed by monitoring the frequency, duration, and severity of adverse events (AEs), through physical examinations, by evaluating changes in vital signs and ECGs, and through clinical laboratory blood and urine sample evaluations.
- Phase 2: Objective response rate determined by radiographic disease assessments per mRECIST v1.1.

Secondary Endpoints:

- Phase 1: Objective response rate determined by radiographic disease assessments per mRECIST v1.1.
- Phase 2: Safety and tolerability of the combination as assessed by monitoring the frequency, duration, and severity of AEs, through physical examinations, by evaluating changes in vital signs and ECGs, and through clinical laboratory blood and urine sample evaluations.
- Phases 1 and 2: Durability of response determined by radiographic disease assessment defined as the time from earliest date of disease response until earliest date of disease progression.
- Phases 1 and 2: PFS determined from the date of randomization until disease progression or death.
- Phases 1 and 2: The endpoints for assessment of PK of durvalumab and epacadostat include individual durvalumab and epacadostat concentrations and PK parameters.
- Phases 1 and 2: The endpoints for assessment of immunogenicity of durvalumab include the number and percentage of subjects who develop detectable anti-drug antibodies.

[REDACTED]
[REDACTED]
[REDACTED]
[REDACTED]
[REDACTED]
[REDACTED]
[REDACTED]

[REDACTED]

[REDACTED]

[REDACTED]

Planned Number of Subjects: Phase 1: Approximately 36 subjects Phase 2: Approximately 140 to 192 subjects

Principal Coordinating Investigator: TBD

Estimated Study Duration: Estimated date first subject enrolled: 29 OCT 2014 Estimated date last subject completed: 25 OCT 2019

Statistical Methods: Up to 36 subjects will be enrolled in the Phase 1 dose-escalation portion of the study and approximately 140 to 192 subjects will be enrolled in Phase 2 based on the Simon 2-stage design and expansion cohorts in select solid tumors. Descriptive statistics (eg, mean, standard deviation, range) will be derived where appropriate. Subject enrollment, disposition, demographics, and medical history will be summarized at baseline. The rate of DLTs will be summarized for each cohort. Dose exposure and density will be calculated for each cohort. Objective response rate will be summarized. Median duration of response and PFS will be analyzed by the Kaplan-Meier method. Pharmacokinetic [REDACTED] data will be analyzed with appropriate standard nonlinear analytic software.

TABLE OF CONTENTS

SYNOPSIS	3
LIST OF ABBREVIATIONS.....	20
1. INTRODUCTION	23
1.1. Pharmaceutical and Therapeutic Background	23
1.1.1. Inhibition of PD-1 Signaling as a Target for Cancer.....	23
1.1.2. Inhibition of IDO1 as a Target for Cancer.....	24
1.1.3. Epacadostat	25
1.1.4. Durvalumab	26
1.1.5. Combined Immune Checkpoint Inhibition	26
1.1.6. Melanoma	28
1.1.7. Non–Small Cell Lung Cancer	29
1.1.8. Pancreatic Cancer	31
1.1.9. Squamous Cell Carcinoma of the Head and Neck.....	32
1.1.10. Triple-Negative Breast Cancer	32
1.1.11. Gastric and Gastroesophageal Junction Cancer.....	33
1.1.12. Transitional Cell Carcinoma of the Genitourinary Tract.....	34
1.1.13. Preclinical and Clinical Study Data.....	35
1.1.13.1. Summary of Epacadostat Pharmacokinetics in Humans	35
1.1.13.2. Summary of Epacadostat Pharmacodynamics in Humans	36
1.1.13.3. Summary of Durvalumab Pharmacokinetics in Humans.....	38
1.2. Study Rationale.....	38

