20. History or presence of an abnormal ECG that, in the investigator's opinion, is clinically meaningful. Screening QTc interval > 480 msec is excluded (corrected by Fridericia or Bazett's formula). In the event that a single QTc is > 480 msec, the subject may be enrolled if the average QTc for the 3 ECGs is \leq 480 msec. For subjects with an intraventricular conduction delay (QRS interval \geq 120 msec), the JTc interval may be used in place of the QTc with sponsor approval. The JTc must be < 340 msec if JTc is used in place of the QTc. Subjects with left bundle branch block are excluded.
21. Clinically significant cardiac disease, including unstable angina, acute myocardial infarction within 6 months from Day 1 of study drug administration, New York Heart Association Class III or IV congestive heart failure, and arrhythmia requiring therapy.
- Note: A subject with an arrhythmia may enroll if the subject is on anti-arrhythmic medication and is in sinus rhythm on the screening ECG.*
22. Any prior \geq Grade 3 irAE while receiving immunotherapy, including anti-PD-1, anti-PD-L1, or anti-CTLA-4 treatment, or any unresolved irAE > Grade 1. Must not have experienced a toxicity that led to permanent discontinuation of prior immunotherapy. Subjects with endocrine AEs \leq Grade 2 are permitted to enroll if they are stably maintained on appropriate replacement therapy and are asymptomatic. Subjects with prior anti-PD-1, anti-PD-L1, or anti-CTLA-4 therapy must not have required the use of additional immunosuppression other than corticosteroids for the management of an AE, not have experienced recurrence of an AE if rechallenged, and not currently require maintenance doses of > 10 mg prednisone or equivalent per day.
- Note: Previous immune-related ocular or neurologic toxicity of any grade is excluded.*
23. Known allergy or reaction to any component of either study drug formulation.
24. Subjects who require ongoing thoracentesis or paracentesis for palliation must be discussed with the medical monitor to determine eligibility.
25. History of primary immunodeficiency.
26. History of leptomeningeal carcinomatosis.

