## 8.5. Electrocardiograms

Twelve-lead ECGs will be obtained for each subject during the study in accordance with [Table 5](#). Electrocardiogram results will be reviewed for clinically notable abnormalities according to predefined criteria (see [Table 13](#)). Electrocardiogram abnormalities, both at baseline and postbaseline visits, will be tabulated by treatment group. Incidences of abnormalities will be listed with study visit, assigned treatment group, and a description of the abnormality.

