3.5.2.2	Summary of 12-Lead ECG: QRS Interval Values	Phase 2 Safety	X	

Table No.	Title	Population	Standard	In-Text
3.5.3.1	Summary of 12-Lead ECG: QT Interval Values	Phase 1 Safety	X	
3.5.3.2	Summary of 12-Lead ECG: QT Interval Values	Phase 2 Safety	X	
3.5.4.1	Summary of 12-Lead ECG: QTcB Interval Values	Phase 1 Safety	X	
3.5.4.2	Summary of 12-Lead ECG: QTcB Interval Values	Phase 2 Safety	X	
3.5.5.1	Summary of 12-Lead ECG: QTcF Interval Values	Phase 1 Safety	X	
3.5.5.2	Summary of 12-Lead ECG: QTcF Interval Values	Phase 2 Safety	X	
3.5.6.1	Summary of 12-Lead ECG: RR Interval Values	Phase 1 Safety	X	
3.5.6.2	Summary of 12-Lead ECG: RR Interval Values	Phase 2 Safety	X	
3.5.7.1	Summary of Treatment Emergent, Clinically Significant ECG Abnormality from Baseline	Phase 1 Safety		X
3.5.7.2	Summary of Clinically Notable ECG Abnormalities	Phase 2 Safety		X

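### SAP Table 13 flags QTcF above 460 ms and QRS above 120 ms with no baseline condition, though eligible subjects can enter with such values, so the Phase 2 ECG count mixes carried-over with new abnormalities

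*Protocol*

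**What the plan says.** **Entry.** The Synopsis (Key Exclusion Criteria) and Protocol 3.3, criterion 20, give the limit as "Screening QTc interval > 480 msec is excluded", with correction by either Fridericia or Bazett. A single value above 480 ms can be averaged over three ECGs. For subjects with QRS of 120 ms or more, "the JTc interval may be used in place of the QTc with sponsor approval".

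**Analysis.** SAP 8.5 says: "Electrocardiogram results will be reviewed for clinically notable abnormalities according to predefined criteria". Those criteria are in Table 13, where the high limits include QTcF above 460 ms (Fridericia only) and QRS above 120 ms. SAP 8.5 continues: "Electrocardiogram abnormalities, both at baseline and postbaseline visits, will be tabulated by treatment group". It does not require a change from baseline or a normal baseline value.

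**Planned tables (SAP Appendix C).** The Phase 2 table, 3.5.7.2, is titled "Summary of Clinically Notable ECG Abnormalities". The title of its Phase 1 counterpart, 3.5.7.1, refers to treatment-emergent, clinically significant abnormality from baseline.

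**Endpoint.** Safety is to be assessed, among other means, "by evaluating changes in vital signs and ECGs".

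**Status of the SAP.** SAP 2.1 bases the plan on Protocol Amendment 1 and keeps it in force for later amendments unless superseded. SAP Table 15 lists only the original version of 26 NOV 2014. According to the protocol's amendment summary, the 480 ms limit came in with Amendment 4, after that date.

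**The concern.** The analysis limit lies inside the range that eligibility allows. A subject can be acceptable for entry and already clinically notable before the first dose. With no baseline condition, that subject is counted again after dosing even if nothing has changed. A reader of the in-text Phase 2 table would take the post-baseline count as ECG findings that arose on study, when part of it describes who was enrolled.

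The SAP avoids this elsewhere. SAP 8.3.2 counts laboratory abnormalities by treatment-emergent worsening of grade, and its worked glucose example leaves out a subject whose grade was already raised at baseline and did not increase. SAP 8.4 defines a vital-sign alert as a value outside the range together with a change of more than 25%. ECGs are the exception, although the endpoint is worded in terms of changes.

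**Working it through.** **1. The two limits for a Fridericia-screened subject.** 480 − 460 = 20 ms. Values of 461 to 480 ms are eligible and notable at once. For QRS, the JTc route starts at 120 ms and the Table 13 flag applies above 120 ms, so subjects admitted by that route with QRS above 120 ms are flagged from the start.

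**2. A Bazett-screened subject.** Since QTcB = QT/RR^(1/2) and QTcF = QT/RR^(1/3), QTcF = QTcB × RR^(1/6), with RR = 60/heart rate. For QTcB = 480 ms:

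| Heart rate (bpm) | QTcF (ms) |
|---|---|
| 50 | 494.8 |
| 60 | 480.0 |
| 70 | 467.8 |
| 77.5 | 460.0 |
| 80 | 457.5 |
| 90 | 448.6 |

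The crossover solves RR = (460/480)^6 = 0.7746, which is 60/0.7746 = 77.5 bpm. Above that rate, a subject admitted at a Bazett value of 480 ms or less is below the Table 13 limit. Below it, the overlap remains.

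**3. Subjects with no change.** At QTcF of 461, 465, 470 or 480 ms before and after dosing, the current rule flags the subject at baseline and again post-baseline. With the added condition that baseline is at or below 460 ms, none of them is counted as new. A subject at 455 ms throughout is not flagged under either rule.

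**4. Size, under assumptions.** The documents give no QTcF distribution, so these inputs are assumed: mean 415 to 425 ms, between-subject SD 18 to 20 ms, within-subject SD 8 to 10 ms, normal errors, no drug effect. The baseline reading is truncated at 480 ms. Protocol Table 27 gives eight ECGs after the first dose: two on Cycle 1 Day 1, three on Cycle 2 Day 1, one at end of treatment and two at safety follow-up.

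The share starting above 460 ms follows from the normal distribution. The SD of a single reading is √(between² + within²).

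- (415, 18, 8): SD 19.7. P(>460) = 1.12%, P(>480) = 0.05%, so (1.12 − 0.05)/0.9995 = 1.1%.
- (420, 20, 8): SD 21.5. (3.17 − 0.27)/0.9973 = 2.9%.
- (425, 20, 10): SD 22.4. (5.88 − 0.70)/0.9930 = 5.2%.

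The remaining shares come from simulating 600,000 subjects per scenario:

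| Mean, SD between, SD within | Baseline >460 | Any of 8 readings >460 (current rule) | Same, baseline ≤460 required | Of those flagged, share already >460 at baseline |
|---|---|---|---|---|
| 415, 18, 8 | 1.1% | 3.5% | 2.7% | 25% |
| 420, 20, 8 | 2.9% | 8.0% | 5.5% | 32% |
| 425, 20, 10 | 5.2% | 15.5% | 10.9% | 29% |

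Repeat runs give 15.4 or 15.5% in the third row. On the upper planned Phase 2 size of 192, the current rule flags 192 × 3.5% ≈ 7 to 192 × 15.5% ≈ 30 subjects. The baseline condition leaves 192 × 2.7% ≈ 5 to 192 × 10.9% ≈ 21. Those remaining start at or below 460 ms and cross it by chance on at least one of eight readings.

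**The case against.** Much of the information is already in the planned output. SAP 8.5 tabulates abnormalities at baseline as well as post-baseline and lists them by visit. Listings 16.2.11.1 and 16.2.11.2 hold all ECG values and the abnormal ones. Table 3.5.5.2 summarises Phase 2 QTcF. A subject at 470 ms before and after dosing can be traced. This stands, and it limits the harm. It does not repair the in-text count, because separate baseline and post-baseline totals do not show which post-baseline cases are new.

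A reader might also infer more than the documents support:

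- **That the limit mismatch produces most of the no-effect flags.** It does not. In these scenarios 68 to 75% of flagged subjects start at or below 460 ms.
- **That a baseline condition would almost clear the table.** No-effect rates of 0.2 to 2.2% arise only under a three-part rule applied at one reading: baseline at or below 460 ms, value above 460 ms and a rise of at least 30 ms. A baseline condition alone does not give them.
- **That the two phases demonstrably use different rules.** The difference rests on table titles. The visible shell for 3.5.7.1 has no row excluding baseline abnormalities, and its wording, clinically significant, is not the Table 13 term. No shell for 3.5.7.2 is visible, so what it would show is unknown.
- **That a primary endpoint or decision rule is at risk.** Table 13 does not enter the dose-limiting toxicity criteria (Protocol Table 7) or the Phase 2 suspension rule (Protocol 9.6).
- **That every flag arises on treatment.** Two of the eight ECGs are safety follow-up visits, 42 and 90 days after the end-of-treatment visit.

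**Conclusion.** The point holds as a limited one. As SAP 8.5 and Table 13 are written, subjects with QTcF of 461 to 480 ms or QRS above 120 ms at entry and no later change are counted as clinically notable post-baseline in the Phase 2 summary. This follows from the text alone and departs from the SAP's own laboratory and vital-sign conventions. The overlap disappears for Bazett-screened subjects with heart rates above about 77.5 bpm.

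The size is assumption-based. With no drug effect, about 1 to 5% of subjects start above 460 ms and 3.5 to 15.5% are flagged; a baseline condition brings the second range to about 2.7 to 10.9%. All of these figures move with the assumed mean and SDs. They also treat the screening limit as applying to the SAP baseline, which is the last value before the first dose (SAP 4.1.4), and they ignore the averaging and JTc routes.

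The consequence is confined to a descriptive safety table. Dose-limiting toxicities, the safety suspension rule, ORR and sample size are unaffected. The change is worth making because it is cheap and makes the table reflect change on study.

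**What to change.** In SAP 8.5 and in Tables 3.5.7.1 and 3.5.7.2:

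1. State one rule for both phases. A subject is treatment-emergent notable for a parameter only if the baseline value is within the Table 13 limit and a post-baseline value is outside it.
2. Show subjects already outside a limit at baseline, including those with QRS above 120 ms, in a shift table from baseline to worst post-baseline value.
3. Add a categorical summary of QTcF change from baseline, with categories fixed in the SAP before the table is run. A baseline condition leaves most chance crossings in the count, so this summary is needed as well.
4. Reconcile the Table 13 QTcF limit with the 480 ms entry limit, and note that eligibility allows Bazett while Table 13 uses Fridericia. Which limit is clinically right is for the sponsor.

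The cost is SAP wording, reprogramming of the notable-ECG table and a slightly longer ECG output. The data are already collected.
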